### **11.1.** Safety and Efficacy Assessments

The safety and efficacy of APL-9 treatment will be assessed by objective endpoints and compared between treatment groups. These endpoints relate to AEs, overall hospitalization, use of mechanical ventilation and oxygen, assessments of organ failure, and overall survival. The SoA (Table 1) provides details of the scheduling of these assessments.

Assessments to be performed during the study are described below and in the SoA (Table 1). Every effort should be made to ensure that the protocol-required assessments are completed as described.

If deemed necessary, additional safety measurements will be performed at the discretion of the investigator.

#### 11.1.1. SOFA Score

Organ failure status will be assessed using the SOFA score, which assesses 6 organ systems: respiration, coagulation, liver, cardiovascular, central nervous system, and renal (Ferreira et al. 2001). A subject will be defined as being free of organ failure when the SOFA score is zero. The score will be assessed at baseline on Day 1 and as listed in the SoA based on worst daily values.

The SOFA score variables to be assessed are:

- PaO2/FiO2 ratio (mm Hg) or SpO2/FiO2 ratio—collected and entered into the database locally (see calculation instructions in Appendix 1)
- Platelets  $\times 10^3/\mu$ L—based on data provided by the local laboratory
- Bilirubin ( $\mu$ mol/L or mg/dL)—based on data provided by the local laboratory
- Hypotension/use of vasopressors—collected and entered into the database locally
- Glasgow Coma Scale score—collected and entered into the database locally (see Appendix 2)
- Creatinine (µmol/L or mg/dL)—based on data provided by the local laboratory

See Appendix 1 for additional information on calculating the SOFA score.

#### 11.1.2. Computed Tomographic Scans/Radiographs: Pulmonary Consolidation

Pulmonary consolidation is defined as presence or absence of alveolar opacity observed in chest computed tomographic scans or radiographs in each of the 4 lung quadrants (left upper, left lower, right upper, and right lower), as determined by the investigator.

#### 11.1.3. Demographic/Medical History

Relevant medical history will be recorded at screening. Investigators should document the occurrence, signs, and symptoms of the subject's preexisting conditions, including all prior significant illnesses, up to and including 1 year before screening. Additional preexisting conditions present at the time when informed consent is given up to the time of first dosing are to be regarded as concomitant. Medical history will include alcohol consumption and smoking history, if applicable. Vaccination history should be attempted to be collected as a component of medical history.

Illnesses first occurring or detected during the study and/or worsening of a concomitant illness during the study are to be documented as AEs on the eCRF in accordance with Section 11.2.5.

Additionally, demographic data will be collected for all subjects, as allowed per applicable regulations.

#### 11.1.4. Assessment of Kidney and Liver Failure

Evidence of kidney and liver failure will be assessed at screening using the following parameters:

- Estimated glomerular filtration rate <45 mL/min/1.73 m^2 AND
- Alanine aminotransferase more than 5 times the upper limit of normal

#### 11.1.5. Vital Signs

Vital signs (body temperature, respiration rate, heart rate, and systolic and diastolic blood pressure measurements) will be evaluated at the visits indicated in the SoA (Table 1). All vital signs will be measured after the subject has been resting in a sitting/prone position for at least 5 minutes, except when they are supine or semireclined because of study procedures and/or AEs, or if deemed necessary by the investigator. Blood pressure measurements are to be taken in the same arm for the duration of the study.

Vital signs measurements will be repeated if clinically significant or if machine/equipment errors occur. Out-of-range blood pressure, respiratory rate, or heart rate measurements will be repeated at the investigator's discretion. Any confirmed, clinically significant changes in vital signs measurements must be recorded as AEs.

#### 11.1.6. Weight and Height

Body weight and height will be noted at screening and can be as estimated by the subject.

#### 11.1.7. Infusion Site/Pump Safety Assessment

Study drug will be administered by trained and qualified site staff. All clinically significant findings related to injection/infusion procedures will be recorded as AEs.

#### 11.1.8. Clinical Laboratory Tests

Laboratory test samples (Table 2) are to be obtained at designated visits as detailed in the SoA (Table 1). Blood will be collected 3 times on Day 1: (1) once prior to administration of the APL-9 bolus, (2) once as soon as possible following the bolus (within 5-10 minutes) prior to the continuous infusion, and (3) once at 2 hours after the beginning of the continuous infusion. Following that, assessments should be collected within the time frame of each calendar day.

Blood samples will be analyzed at one or more central (or local) laboratory facilities, as defined in the laboratory manual. All laboratory reports must be reviewed, signed, and dated by the investigator. A legible copy of all reports must be filed with both the subject's eCRF and medical record (source document) for that visit. Any laboratory test result considered by the investigator to be clinically significant should be considered an AE (clinically significant AEs include those that at minimum require an intervention). Clinically significant abnormal values occurring during the study will be followed up until repeat test results return to normal, stabilize, or are no longer clinically significant.

Instructions for collection, handling, processing, storage, and shipping of samples will be provided in a separate laboratory reference manual prior to study initiation.

PARAMETERS ANALYZED AT	THE LOCAL LABORATORY	
Blood/serum/plasma samples		
Hematology	Serum chemistry	
ABG	Albumin	Ferritin
Hb	ALT	Glucose
Hematocrit	ALP	Haptoglobin
Platelet count	AST	HDL
RBC count	Bicarbonate	Iron
Reticulocyte count	Bilirubin (total, direct, and indirect)	LDH
Schistocytes	BUN	LDL
WBC count with differential	C-reactive protein (CRP)	Phosphorus
	C3 and C4	Potassium
Coagulation panel a	Calcium	Pregnancy
D-dimer	Chloride	Sodium
Fibrinogen	Creatinine	Total cholesterol
INR	Creatine kinase	Total protein
PT	Cystatin C	Triglycerides
	eGFR	Troponin
		Uric acid
Urine samples		
Urinalysis		
Bilirubin		Nitrite
Blood		pН
Glucose		Protein
Ketones		Specific gravity
Leukocyte esterase		Urobilinogen
-	sediment, including for presence of	
	performed on all abnormal urinalyses	
Respiratory swab	· · · · · ·	
Viral RNA or viral antigen assessme	nt	
SARS-CoV-2		
PARAMETERS ANALYZED AT	CENTRAL/SPECIALTY LABORATO	RIES
Plasma samples		
Complement biomarkers	Inflammation biomarkers CC	
Bb, C3a, C4a, C5a, TCC	TNFα	
	IL-1β	
	IL-6	
Serum samples		
PK concentrations		
AH50		
	ACR = albumin-to-creatinine ratio: AH50 = alt	

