## Table 1:Schedule of Assessments

	Study Day(s) a													
	Part 1 and Part 2 a								Pa	art 2 onl	y a	Part 1 and Part 2 a		
List of activities/assessments	Screening/baseline —7 to 1 b	2	3	4	5	6	7	8-10	11	12-14	15	16-21	EOT and discharge day a,n	Safety follow- up assessment a Up to and including Study Day 51 (+7)
Informed consent b	Х													
Inclusion/exclusion b	Х													
SARS-CoV-2 confirmation c	Х													
Medical history 	Х													
Demographics	Х													
eGFR/ALT	Х													
Serum pregnancy test	Х													
Height/body weight/BMI d	Х													
Randomization (Part 2 only)	Х													
Study drug administration a	Х	Х	Х	Х	Х	Х	Χ	Х	X	X	Х	Х	Х	
Discharge card dispensation e													Х	
SAFETY ASSESSMENTS														
Vital signs f	Х	Х	Х	Х		Х	Χ	Х	X	X	Х	Х	Х	
ECG f	Х	Х	Х	Х		Х	Χ	Х	X	X	Х	Х	Х	
SOFA score g	Х		Х		Х		Χ		X		Х		Х	
Clinical laboratory tests h	Х		Х		Х		Χ		X		Х		Х	
Viral RNA or viral antigen assessment k	Х						Χ				Х		Х	
Radiograph/CT scan (pulmonary consolidation)	Х						Χ						Х	
Concomitant medications and procedures i	Х	Χ	Х	Х		Х	Χ	Х	X	X	Х	X	Х	Х
Infusion site reactions j	Х	Х	Х	Х		Х	Χ	Х	X	X	Х	Х	Х	Х
Adverse events	Х	Х	Х	Х	Х	Х	Χ	Х	X	X	Х	X	Х	Х
PHARMACODYNAMIC AND PHARMACOKINETIC ASSESSMENTS														
PK (APL-9)/PD (complement, coagulation, and inflammation)	X		Х		X		Х		Х		Х		$X^{m}$	

Abbreviations: ABG = arterial blood gas; AE = adverse event; ALT = alanine aminotransferase; ARDS = acute respiratory distress syndrome; BMI = body mass index; CT = computed tomographic; DMC = data monitoring committee; ECG = electrocardiogram; eGFR = estimated glomerular filtration rate; EOT = endof-treatment visit;  $FiO_2$  = fraction of inspired oxygen; GCS = Glasgow Coma Scale; ICU = intensive care unit;  $PaO_2$  = partial pressure of oxygen; PD = pharmacodynamics; PK = pharmacokinetics; SAE = serious adverse event; SARS-CoV-2 = severe acute respiratory syndrome coronavirus 2; SOFA = Sequential Organ Failure Assessment;  $SpO_2$  = peripheral oxygen saturation.

Apellis Pharmaceuticals, Inc

#### APL-9 APL9-COV-201 Protocol Amendment 3

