- b Fully eligible subjects can have screening assessments on the same day as baseline, which is defined as the day of initial study drug treatment.
- c Confirmation of SARS-CoV-2 infection may be completed more than 7 days before baseline. Presence of SARS-CoV-2 viral RNA or viral antigen may be detected in respiratory specimens (collected using nasopharyngeal or oropharyngeal swabs) with a qualitative nucleic acid amplification test (such as reverse transcriptase polymerase chain reaction), viral antigen test, or other diagnostic method that is authorized, cleared, or approved by the US Food and Drug Administration or equivalent authority for SARS-CoV-2 viral detection. Note: Serology-based antibody tests do not detect presence of virus and therefore are not considered diagnostic for active infection and cannot be used for study eligibility screening or for subsequent SARS-CoV-2 assessments.
- d Height/weight can be by subject assertion.
- e Discharged subjects who are followed up by phone will be provided with emergency study cards that include a list of symptoms associated with infections. The study card also guides subjects with instructions to contact their study physicians or seek emergency medical care if they experience any of the listed symptoms.
- f For continuous variables, the worst observed daily value will be recorded. Vital signs and ECG must be collected between the administration of the loading dose of study treatment and the initiation of the maintenance dose.
- g SOFA score variables (PaO2/FiO2 ratio or SpO2/FiO2 ratio, platelets, bilirubin, hypotension/vasopressor use, GCS score, creatinine) are detailed in Section 11.1.1 and Appendix 1.
- h A list of laboratory assessments is provided in Section 11.1.8. Blood will be collected 3 times on Day 1: (1) once prior to administration of the APL-9 bolus, (2) once as soon as possible following the bolus (within 5-10 minutes) prior to the continuous infusion, and (3) once at 2 hours after the beginning of the continuous infusion. Following that, assessments should be collected within the time frame of each calendar day. The use of silica reagents in coagulation panels should be avoided in subjects treated with APL-9.

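### Protocol 11.1.8 has the investigator sign and file every laboratory report, Table 2 includes APL-9 concentrations and AH50, and nothing exempts these results in blinded Part 2

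*Protocol*

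**What the plan says.** Protocol Section 11.1.8 begins with the samples listed in Table 2 and says they may be analysed at central or local laboratories. It then sets two rules without exception: "All laboratory reports must be reviewed, signed, and dated by the investigator", and "A legible copy of all reports must be filed with both the subject's eCRF and medical record (source document) for that visit". It adds: "Any laboratory test result considered by the investigator to be clinically significant should be considered an AE".

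The central and specialty part of Table 2 lists "PK concentrations" and AH50 under serum, and "Bb, C3a, C4a, C5a, TCC" under plasma, together with the inflammation markers TNFα, IL-1β and IL-6.

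The schedule of assessments has a safety row for clinical laboratory tests and a separate block headed "PHARMACODYNAMIC AND PHARMACOKINETIC ASSESSMENTS". The footnote on the safety row reads: "A list of laboratory assessments is provided in Section 11.1.8".

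Section 9.3.2 and SAP 3.4 keep investigators, study personnel, data management and biostatistics blinded in Part 2. The exceptions are the site pharmacist, the independent statistician, the DMC through its unblinded outputs, and emergency unblinding.

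**The concern.** The two sets of instructions cannot both be followed as written. If every Table 2 report goes to the investigator for signature and into the eCRF, blinded staff at the site, in data management and in statistics receive results that reveal the arm.

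The primary endpoint is the incidence of treatment-emergent SAEs and TEAEs (Section 6.2.1). Relatedness is not part of its definition, so the main route for bias is whether an event is recognised and recorded at all. Section 11.1.8 opens that route directly, because the investigator's own judgement of clinical significance turns a laboratory result into an AE. Causality (Section 11.2.4), which feeds the treatment-related tables in SAP 7.1, would also be judged with the arm known. If results came back quickly enough, so would the investigator's discretionary decision on treatment beyond Day 7.

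**Working it through.** The plan gives no figure to reproduce. The check sets the passages side by side and then makes two counts.

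**1. Does the sign-off rule reach the PK and complement results?** Section 11.1.8 takes Table 2 as its scope, names central as well as local laboratories, and applies to all reports. Table 2 contains the APL-9 concentration and AH50. The footnote on the safety row of the schedule sends the reader to the whole 11.1.8 list, not to its safety part.

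**2. Is there an exemption elsewhere?** Protocol 7.2, 9.3.2, 11.5, 11.6, 12.2.6 to 12.2.8 and 12.7 were read for one, as were SAP 3.4, 4.5, 4.6, 7.2, 8, 9 and 11. Sections 11.5 and 11.6 cover sampling times, tubes and, for PK, storage and shipping. SAP 8 and 9 describe summaries and listings by treatment group. None of these says who may see the results or when.

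**3. Do the results reveal the arm?**
- APL-9 concentration: the vehicle bags contain no APL-9 (Synopsis, Study Drug Treatments, Part 2), so a measurable value identifies active treatment.
- AH50: this measures alternative-pathway haemolytic activity. Section 5.2 describes APL-9 as potently inhibiting all three pathways, and Section 7.3 says the regimen is chosen to keep complement suppressed throughout dosing. A suppressed AH50 is therefore strongly indicative, although the documents give no AH50 values.
- Bb, C3a, C4a, C5a, TCC: the documents give no size of response, so their power to reveal the arm is unknown.

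**4. Count of central and specialty parameters** (legible entries only; redacted ones not counted):
- Bb, C3a, C4a, C5a, TCC = 5
- TNFα, IL-1β, IL-6 = 3
- APL-9 concentration, AH50 = 2
- Total 5 + 3 + 2 = 10. Drug concentration or complement measures: 5 + 2 = 7 of 10.

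**5. Range of subjects whose arm could become known in Part 2:**
- Lower end: 0, if no central report is released before unblinding.
- Upper end: about 30 on APL-9 (drug present) + about 30 on vehicle (drug absent) = about 60, if every report is handled as 11.1.8 says. This assumes that APL-9 is measurable during infusion.

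**The case against.** The strongest reply is that 11.1.8 is meant for safety laboratories only. Its title is Clinical Laboratory Tests, PK and PD have their own sections (11.5, 11.6) with no sign-off rule, and the schedule separates the two. Following abnormal values until they return to normal makes sense for a safety test and not for a drug concentration. Filing by visit also suits local reports better than frozen serum shipped on dry ice. This reading is possible and may be what was intended, but no sentence says so, and both the opening of 11.1.8 and the schedule footnote point to the whole of Table 2.

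SAP 7.2 is weak support for the wider reading. It takes Table 2 as its laboratory list and names complement activation among the laboratory data. However, it refers to local normal ranges, and the locally measured C3 and C4 could satisfy it. The conclusion does not depend on it.

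A second reply is that the specific blinding duty in 9.3.2 overrides a general reporting sentence, and that the laboratory manual may restrict release. The manual was not available. The protocol describes its instructions as covering collection, handling, processing, storage and shipping, not release of results. If it does hold these results back, it contradicts the protocol's rule on all reports, and the protocol still needs correcting.

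A third reply is that harm requires reports to reach sites in time, be read, and change behaviour. That stands. No passage says whether or when central results return, and an effect on the Day 7 decision would need a turnaround of about a week. It limits what can be said about consequences but does not remove the conflict.

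**Conclusion.** The concern holds. The protocol contains a rule that would unblind Part 2 if followed, and neither document withdraws it for the APL-9 concentration, AH50 or the other central complement markers. One parameter identifies the active arm if measurable, one is strongly indicative, and five are of unknown strength. Between 0 and about 60 subjects could be affected, and the documents do not narrow that range. The upper end rests on the assumption that APL-9 is measurable during infusion. There is no evidence that unblinding took place. The change should be made because the primary endpoint depends on investigator-reported events and the correction is cheap. Confidence is medium, because the safety-only reading is available and the laboratory manual has not been seen.

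**What to change.** - Limit the review, signature and filing rule in 11.1.8 to safety laboratory reports.
- State that in Part 2 the post-dose APL-9, AH50, Bb, C3a, C4a, C5a and TCC results stay with the central or specialty laboratory. They are not released to sites, the eCRF, or blinded sponsor, data-management or statistics staff before authorised unblinding. Put the same rule in the laboratory manual.
- Leave DMC access as it is, through the unblinded outputs in 9.3.2.
- For the pre-lock review in 12.2.8, use masked sample status (collected, evaluable), coded identically in both arms, in place of values. This is enough for the PK set, which needs one evaluable sample (12.2.6).
- Ask the sponsor to confirm whether locally measured C3 can reveal the arm. The documents do not give its response to APL-9.

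The cost is wording in the protocol and laboratory manual, plus a masked status transfer from the central laboratory. No new samples, visits or roles are needed. The drawback is that blinded staff cannot check the held values for outliers before unblinding, so 12.2.8 should say that this check is deferred for them.

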#### Table 2: **Clinical Laboratory Tests**

Abbreviations: ABG = arterial blood gas; ACR = albumin-to-creatinine ratio; AH50 = alternative complement pathway

hemolytic activity; ALP = alkaline phosphatase; ALT = alanine aminotransferase; <math>COIAST = aspartate aminotransferase; BCR = B-2 microglobulin:creatinine ratio; BUN = blood urea nitrogen; eGFR = estimated glomerular filtration rate; Hb = hemoglobin; HDL = high-density lipoprotein; INR = international normalized ratio; LDH = lactate dehydrogenase; LDL = low-density lipoprotein; PK = pharmacokinetics; PT = prothrombin time; RBC = red blood cell; SARS-CoV-2 = severe acute respiratory syndrome coronavirus 2; TCC = terminal complement complex; TNF $\alpha$  = tumor necrosis factor  $\alpha$ ; WBC = white blood cell.

a The use of silica reagents in coagulation panels should be avoided in subjects treated with APL-9.

#### 11.1.8.1. Pregnancy Screening

For women of childbearing potential, a serum pregnancy test will be performed at screening. Subjects with a positive test result will be excluded or discontinued from the study.

## **11.2.** Adverse Events

#### **11.2.1. Definition of AEs**

An AE is any untoward medical occurrence associated with the use of a drug in humans, whether or not it is considered drug related. An AE can, therefore, be any unfavorable and unintended sign, including a clinically significant abnormal laboratory finding, symptom, or disease temporally associated with the use of an investigational product, whether or not considered related to the investigational product.

Adverse events can be spontaneously reported by the subject and/or in response to an open question from the study personnel or revealed by observation and will be recorded during the study at the investigational site. All identified AEs must be recorded and described on the appropriate AE or SAE page of the eCRF.

Fluctuating or nonsignificant changes in laboratory values do not necessarily qualify for AE reporting. If these changes in laboratory values are assessed as clinically significant and/or lead to discontinuation of administration of investigational product, these should be reported as an AE. If these laboratory values are linked to a diagnosis, only the diagnosis should be reported as AE.

#### 11.2.2. Serious Adverse Events

An SAE is any AE or suspected adverse reaction that, in the view of either the investigator or sponsor, results in any of the following outcomes: death; life threatening; inpatient hospitalization or prolongation of existing hospitalization; a persistent or significant incapacity or substantial disruption of the ability to conduct normal life functions; or a congenital anomaly/birth defect.

Important medical events that may not result in death, be life threatening\*, or require hospitalization may be considered serious when, based upon appropriate medical judgment they may jeopardize the subject and may require medical/surgical intervention to prevent one of the outcomes listed in the above definition.

Examples of important medical events include allergic bronchospasm requiring intensive treatment in an emergency room or at home; blood dyscrasias or convulsions that do not result in inpatient hospitalization; or the development of drug dependency or drug abuse.

\**Life threatening* is defined as an AE or suspected adverse reaction, which, in the view of either the investigator or sponsor, places the subject at immediate risk of death as it occurred. It does not include an AE or suspected adverse reaction that, had it occurred in a more severe form, might have caused death.

#### 11.2.3. Unexpected Adverse Events

An AE is considered "unexpected" if it is not listed in the Reference Safety Information section of the investigator's brochure in effect at that time of event onset.

#### **11.2.4.** Evaluation of AEs

All AEs that occur during this study will be recorded; however, only TEAEs will be analyzed and reported in the study report. The investigator or their medically qualified designee will review each event and assess its relationship to study drug treatment (not related, unlikely to be related, possibly related, or definitely related). The date and time of onset, time relationship to study drug dosing, duration, and outcome (recovered/resolved, recovered/resolved with sequelae, recovering/resolving, not recovered/not resolved, or fatal) of each event will be noted.

Table 3 should be considered when evaluating the relationship of AEs/SAEs to study treatment.

 Table 3:
 Definitions of Adverse Event Relatedness

Classification	Definition
Definitely related	Strong evidence of a causal relationship; the influence of other factors is unlikely
Possibly related	Some evidence of a causal relationship, but other factors may have caused or contributed to the event (eg, another illness or concomitant treatment)
Unlikely to be related	A causal relationship is not a reasonable possibility, but it cannot be completely ruled out with the available evidence
Not related	No evidence of a causal relationship

If the AE/SAE is determined to be possibly or definitely related to the study drug, the event will be considered to be related to the study drug for the purposes of expedited regulatory reporting.

Table 4 presents the definitions that should be considered when evaluating the severity of AEs and SAEs.

Severity	Definition/description
Mild	Event results in mild or transient discomfort, not requiring intervention or treatment; does not limit or interfere with daily activities (eg, insomnia, mild headache).
Moderate	Event is sufficiently discomforting so as to limit or interfere with daily activities; may require interventional treatment (eg, febrile illness requiring oral medication).
Severe	Event results in significant symptoms that prevent normal daily activities; may require hospitalization or invasive intervention (eg, anemia resulting in blood transfusion).

